6. STUDY OBJECTIVES

The primary objective of the study is to evaluate the anti-cancer activity of CDX-011 in metastatic, GPNMB over-expressing, triple-negative breast cancer as measured by the duration of progression-free survival (PFS).

Secondary objectives are:

- To further assess the anti-cancer activity of CDX-011 in metastatic, GPNMB over-expressing, triple-negative breast cancer, as assessed by the objective response rate (ORR), duration of response (DOR) and overall survival (OS).
- To further characterize the safety of CDX-011 in metastatic, GPNMB over-expressing, triple-negative breast cancer.
- To obtain pharmacokinetic parameters and to explore the relationships between patient-specific measures of exposure and safety and activity parameters

An exploratory objective is:

- To assess whether treatment with CDX-011 is associated with improvement in quality of life and/or cancer-related pain as reflected by reduced analgesic use.

7. INVESTIGATIONAL PLAN

7.1. Overall Design and Plan of the Study

This is a pivotal, open-label, prospectively controlled, randomized study of CDX-011 in patients with metastatic GPNMB-expressing triple negative breast cancer. Eligible patients will be randomized (2:1) to receive CDX-011 or capecitabine. Enrollment will be stratified as follows:

- 0-1 prior line of chemotherapy for advanced disease vs. 2 prior lines of chemotherapy for advanced disease

- Progression-free interval \leq 6 months after receipt of taxane therapy vs. progression-free interval $>$ 6 months after receipt of taxane therapy
- Received anthracycline therapy previously vs. no prior anthracycline therapy

Study treatment, and associated study visits at 3 week intervals, will continue until disease progression or intolerance. Tumor assessments will be performed at six week intervals for six months and nine week intervals thereafter, until disease progression. Upon discontinuation of study treatment, patients will be permitted to receive appropriate alternate anti-cancer therapies and will be followed for progression-free survival (if progression is not yet documented) and overall survival.

The study analyses of PFS, ORR and DOR will be based on tumor response assessments performed by an independent review committee according to RECIST 1.1 guidelines ([Eisenhauer, Therasse et al. 2009](#)) ([Appendix 3](#)). The investigator's assessment of tumor response (according to RECIST 1.1) will guide clinical management and eligibility for continuation of study treatment.

An independent data monitoring committee will review cumulative data on an interim basis. The interim data reviews may include but are not limited to summaries of adverse events, laboratory values and vital signs. The IDMC will conduct reviews approximately every 6 months, or as frequently as deemed necessary by the IDMC, starting from the first randomized patient. If a safety concern is identified, the IDMC may recommend modifying, halting or permanently stopping the trial at any time.

7.2. Selection of Study Population

7.2.1. Number of Patients

Approximately 300 patients will be enrolled (randomized 2:1 to CDX-011 or capecitabine).

7.2.2. Subject Eligibility

7.2.2.1. Inclusion Criteria

Patients may be included in the study only if they meet all of the following inclusion criteria at the time of randomization:

1. Female or male subjects with metastatic, histologically or cytologically confirmed carcinoma of the breast.
2. Documented progression of disease, based on radiographic, clinical or pathologic assessment showing increased tumor burden or new site(s) of disease during or subsequent to the last anticancer regimen received.
3. Overexpression of GPNMB (\geq 25% of malignant epithelial cells expressing GPNMB, as determined by a central laboratory using IHC methods) in at least one tumor sample obtained in the advanced setting.
4. Triple-negative status confirmed in a tumor sample obtained in the advanced setting, according to the following criteria:
 - a. Minimal or no expression of estrogen and progesterone receptors ($<$ 10% of cells positive by immunohistochemistry (IHC)). Patients with low hormone receptor expression (ER and/or PR 1-9%) must be deemed appropriate candidates for cytotoxic chemotherapy by the investigator.

- b. Minimal or no expression of HER2 (IHC staining of 0 or 1+; ISH single-probe average HER2 copy number < 4.0 signals/cell; or ISH dual-probe HER2/CEP17^b ratio < 2.0 with an average HER2 copy number < 4.0 signals/cell). ([Wolff, Hammond et al. 2014](#))

NOTE: laboratory reports will be required to provide quantitative results of sufficient detail to verify the above eligibility for all patients enrolled.

5. 0 to 2 prior chemotherapy-containing regimens for advanced breast cancer. For the purpose of this criterion, a regimen is defined as any combination of therapy, including sequential therapy, received before progression.
6. Prior receipt of anthracycline-containing chemotherapy in any setting, unless anthracycline therapy is not clinically indicated, in the opinion of the treating investigator.
7. Prior receipt of taxane-containing chemotherapy, in any setting
8. Age \geq 18 years
9. Eastern Cooperative Oncology Group (ECOG) Performance Status 0 to 1 ([Appendix 4](#)).
10. Life expectancy of \geq 3 months.
11. Measurable (target) disease by RECIST 1.1 criteria ([Eisenhauer, Therasse et al. 2009](#)) ([Appendix 3](#)). Target lesions selected for tumor measurements should be those where surgical resection or radiation are not indicated or anticipated.
12. Resolution of all chemotherapy or radiation-related toxicities \leq CTCAE v. 4.0 Grade 1 severity, except for alopecia.
13. Adequate bone marrow function as assessed by absolute neutrophil count (ANC) \geq 1500/mm³; hemoglobin \geq 9.0 g/dL, and platelet count \geq 100,000/mm³.
14. Adequate renal function as assessed by serum creatinine \leq 2.0 mg/dL or calculated creatinine clearance $>$ 40 mL/min per the Cockcroft and Gault formula ([Appendix 5](#)).
15. Adequate liver function as assessed by total bilirubin \leq 1.5 x upper limit of normal (ULN), and alanine transaminase (ALT) and aspartate transaminase (AST) \leq 3.0 x ULN (\leq 5.0 x ULN in the case of liver metastases). Patients with known Gilbert's syndrome may be enrolled with total bilirubin \leq 3.0 mg/dL.
16. Read, understood, and provided written informed consent and, if applicable, HIPAA authorization.

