	
NOTE: laboratory reports will be required to provide quantitative results of sufficient detail to verify the above eligibility for all patients enrolled.
 
5. 0 to 2 prior chemotherapy-containing regimens for advanced breast cancer. For the purpose of this criterion, a regimen is defined as any combination of therapy, including sequential therapy, received before progression.6. Prior receipt of anthracycline-containing chemotherapy in any setting, unless anthracycline therapy is not clinically indicated, in the opinion of the treating investigator7. Prior receipt of taxane-containing chemotherapy, in any setting8. Age \geq 18 years9. Eastern Cooperative Oncology Group (ECOG) Performance Status 0 to 1 (Appendix 4).10. Life expectancy of \geq 3 months11. Measurable (target) disease by RECIST 1.1 criteria (Eisenhauer, Therasse et al. 2009) (Appendix 3). Target lesions selected for tumor measurements should be those where surgical resection or radiation are not indicated or anticipated.12. Resolution of all chemotherapy or radiation-related toxicities \leq CTCAE v. 4.0 Grade 1 severity, except for alopecia.13. Adequate bone marrow function as assessed by absolute neutrophil count (ANC) \geq 1500/mm³; hemoglobin \geq 9.0 g/dL, and platelet count \geq 100,000/mm³.14. Adequate renal function as assessed by serum creatinine \leq 2.0 mg/dL or calculated creatinine clearance $>$ 40 mL/min per the Cockcroft and Gault formula (Appendix 5).15. Adequate liver function as assessed by total bilirubin \leq 1.5 x upper limit of normal (ULN), and alanine transaminase (ALT) and aspartate transaminase (AST) \leq 3.0 x ULN (\leq 5.0 x ULN in the case of liver metastases). Patients with known Gilbert's syndrome may be enrolled with total bilirubin \leq 3.0 mg/dL.16. Read, understood, and provided written informed consent and, if applicable, HIPAA authorization. 
Exclusion Criteria
 
Patients will be excluded from the study for any of the following reasons:
 
1. Progression/recurrence of breast cancer during or within 3 months of completion of neoadjuvant or adjuvant chemotherapy.2. Investigational therapy within four weeks before planned start of study treatment.3. Persistent neuropathy $>$ NCI-CTCAE v. 4.0 Grade 1 (at randomization).4. History of allergic reactions attributed to compounds of similar composition to dolastatin or auristatin. Compounds of similar composition include Auristatin PHE as an anti-fungal agent, Auristatin PE (TZT-1027, Soblidotin, NSC-654663) as an anti-tumor agent and symplostatatin 1 as an anti-tumor agent.5. Known hypersensitivity to 5-fluorouracil, capecitabine or any of its components.6. Known dihydropyrimidine dehydrogenase (DPD) deficiency.7. Known brain metastases, unless previously treated and asymptomatic for 2 months and not progressive in size or number for 2 months prior to randomization. Continued use of steroids and/or anticonvulsants (in the absence of any suspicion of progressive brain metastases) is acceptable.

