11. Active systemic infection requiring treatment. Infection controlled by oral therapy will not be exclusionary. Note: microscopic examination of urinalysis is required during screening. If urinary infection is suspected, then a negative urine culture is required prior to enrollment. ~~{criterion deleted}~~
12. Chronic use of systemic corticosteroid above the physiologic dose (5 mg per day prednisone or equivalent) within 7 days of enrollment, except for premedication. ~~{criterion deleted}~~
13. Significant cardiovascular disease including unstable angina pectoris, uncontrolled hypertension, and congestive heart failure (New York Heart Association class 3 or 4), a history of a serious uncontrollable arrhythmia despite treatment, ischemic or severe valvular heart disease, or a myocardial infarction within 6 months prior to the trial entry.
14. Any underlying medical condition that, in the investigator's opinion, will make the administration of study treatment (CDX-011 or capecitabine) hazardous to the patient, or would obscure the interpretation of adverse events.
15. Other malignancy except for adequately treated and cured basal or squamous cell skin cancer, curatively treated in situ disease, or any other cancer from which the patient has been disease-free for ≥ 5 years.

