8.2. Capecitabine

8.2.1. Description, Packaging, Labeling, Accountability and Storage

Capecitabine will be obtained from commercial supply and handled/stored in a fashion consistent with package insert and institutional policies. Generic capecitabine may be utilized. The following sections are based on package insert recommendations (Feb 2011). However, investigators are responsible for referencing the complete and most current package insert for full guidance regarding potential toxicity and dosing of capecitabine.

Capecitabine is a fluoropyrimidine carbamate with antineoplastic activity. It is an orally administered systemic prodrug of 5'-deoxy-5-fluorouridine (5'-DFUR) which is converted to 5-fluorouracil.

Capecitabine is supplied as biconvex, oblong film-coated tablets for oral administration. Each light peach-colored tablet contains 150 mg of capecitabine and each peach-colored tablet contains 500 mg of capecitabine. The inactive ingredients in capecitabine include: anhydrous lactose, croscarmellose sodium, hydroxypropyl methylcellulose, microcrystalline cellulose, magnesium stearate and purified water. The peach or light peach film coating contains hydroxypropyl methylcellulose, talc, titanium dioxide, and synthetic yellow and red iron oxides.

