8.2.2. Compliance

Compliance with self-administered oral agents (i.e., capecitabine) will be assessed by patient report.

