8.2.3. Administration

Dose Calculation

Capecitabine dose is calculated according to body surface area.

Table 5. Capecitabine Dose Calculation According to Body Surface Area

Dose Level 1250 mg/m ² Twice a Day		Number of Tablets to be Taken at Each Dose (Morning and Evening)	
Surface Area (m ²)	Total Daily Dose* (mg)	150 mg	500 mg
≤ 1.25	3000	0	3
1.26-1.37	3300	1	3
1.38-1.51	3600	2	3
1.52-1.65	4000	0	4
1.66-1.77	4300	1	4
1.78-1.91	4600	2	4
1.92-2.05	5000	0	5
2.06-2.17	5300	1	5
≥ 2.18	5600	2	5

*Total Daily Dose divided by 2 to allow equal morning and evening doses

Dosing and Administration

Investigators are encouraged to follow the recommended dosing from the Capecitabine Package Insert and NCCN Guidelines (available on-line at www.nccn.org), as well as institutional standard. The recommended starting dose of capecitabine per the package insert is 1250 mg/m² administered orally twice daily (morning and evening; equivalent to 2500 mg/m² total daily dose) for 2 weeks followed by a 1-week rest period, given as 3-week cycles. Subsequent treatment will be dictated by tolerance and institutional practice, with consideration to the guidance below.

In patients with moderate renal impairment (baseline creatinine clearance = 40 to 50 mL/min [Cockcroft and Gault; [Appendix 5](#)]), a dose reduction to 75% of the capecitabine starting dose (from 1250 mg/m² to 950 mg/m² twice daily) is recommended. Subsequent dose adjustment is recommended as outlined in [Table 6](#). No adjustment to the starting dose of capecitabine is recommended in patients with mild renal impairment (creatinine clearance = 51 to 80 mL/min).

Capecitabine tablets should be swallowed whole with water within 30 minutes after a meal.

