8.2.6.3. Renal Insufficiency

Patients with moderate (creatinine clearance = 30 to 50 mL/min) and severe (creatinine clearance < 30 mL/min) renal impairment showed higher exposure for capecitabine, 5-FDUR, and FBAL than in those with normal renal function. Patients with moderate renal impairment at baseline require dose reduction (see [Section 8.2.2](#)). Patients with mild and moderate renal impairment at baseline should be carefully monitored for adverse reactions. Prompt interruption of therapy with subsequent dose adjustments is recommended if a patient develops a grade 2 to 4 adverse event as outlined in [Table 6](#).

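### The renal entry rule (inclusion criterion 14) admits patients below 40 and even below 30 mL/min clearance on creatinine alone, while the capecitabine starting-dose text begins at 40 mL/min

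*Protocol*

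**What the plan says.** Criterion 14, in the synopsis and in Protocol 7.2.2.1, begins "Adequate renal function as assessed by serum creatinine" and sets two limits: creatinine no higher than "2.0 mg/dL or calculated creatinine clearance" above 40 mL/min by the Cockcroft-Gault formula in Appendix 5. Meeting either limit satisfies the criterion. None of the exclusions in 7.2.2.2 sets a creatinine or clearance limit.

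Three capecitabine sections bear on the patients this admits:

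- **8.2.3 (Administration)** opens its renal rule "In patients with moderate renal impairment (baseline creatinine clearance = 40 to 50 mL/min" and recommends 75% of the starting dose (950 instead of 1250 mg/m² twice daily). At 51–80 mL/min it recommends no change. It gives nothing below 40.
- **8.2.6.3 (Renal Insufficiency)** uses a wider definition: "Patients with moderate (creatinine clearance = 30 to 50 mL/min) and severe (creatinine clearance < 30 mL/min) renal impairment showed higher exposure for capecitabine". It continues "Patients with moderate renal impairment at baseline require dose reduction (see" and then names Section 8.2.2. It gives no amount, and no instruction on starting dose below 30 mL/min.
- **8.2.2**, the section named there, is Compliance. Its whole content is that "Compliance with self-administered oral agents (i.e., capecitabine) will be assessed by patient report".

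Two general safeguards exist. Exclusion 14 bars a patient with an underlying condition that, in the investigator's opinion, "will make the administration of study treatment (CDX-011 or capecitabine) hazardous to the patient". Section 8.2.1 says that "investigators are responsible for referencing the complete and most current package insert for full guidance regarding potential toxicity and dosing of capecitabine".

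**The concern.** The entry rule and the dosing text do not cover the same patients. Serum creatinine is a weak proxy for clearance in older or lighter women, so a creatinine limit of 2.0 mg/dL joined by 'or' can override the clearance limit beside it. A patient can meet criterion 14 as written, be randomised to capecitabine, and have a clearance at which the protocol itself reports higher drug exposure. Her starting dose, or the decision not to treat her, then rests on the investigator's discretion and an outside document.

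What is at stake is patient safety in the capecitabine arm. The point does not touch the type I error, the power, the event target or the validity of the safety comparison.

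**Working it through.** **Inputs.** The limits are from criterion 14, the dose bands from 8.2.3 and 8.2.6.3, and the formula from Appendix 5. The documents give no distribution of age, weight or creatinine, so the ages and weights below are assumptions. Women are used because the 0.85 factor applies to them; men with the same values have a higher calculated clearance.

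**Formula (women).** Clearance = 0.85 × (140 − age) × weight ÷ (72 × creatinine). Solved for the creatinine at which clearance equals C: creatinine = 0.85 × (140 − age) × weight ÷ (72 × C).

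**Step 1: at what creatinine does clearance reach 40 or 30 mL/min?** For age 65 and 60 kg, the numerator is 0.85 × 75 × 60 = 3825. Then 3825 ÷ (72 × 40) = 3825 ÷ 2880 = 1.33 mg/dL, and 3825 ÷ (72 × 30) = 3825 ÷ 2160 = 1.77 mg/dL. Other examples:

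| Age, weight | 0.85 × (140 − age) × weight | Creatinine at 40 mL/min | Creatinine at 30 mL/min |
|---|---|---|---|
| 55 y, 65 kg | 4696 | 1.63 | 2.17 (above the limit) |
| 60 y, 55 kg | 3740 | 1.30 | 1.73 |
| 65 y, 60 kg | 3825 | 1.33 | 1.77 |
| 70 y, 60 kg | 3570 | 1.24 | 1.65 |

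Every value in the 40 mL/min column is below 2.0 mg/dL, and so are three of the four in the 30 mL/min column. Between the tabulated creatinine and 2.0, the patient fails the clearance limit but still qualifies.

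**Step 2: clearance at the creatinine limit itself.** At 2.0 mg/dL, the 65-year-old, 60 kg woman has 3825 ÷ 144 = 26.6 mL/min. A 70-year-old, 60 kg woman has 3570 ÷ 144 = 24.8. Both satisfy criterion 14.

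**Step 3: how widely does this hold?** Take seven ages (45 to 75 by 5) and six weights (55 to 80 kg by 5), which makes 42 pairs, and apply the formula for women:

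| Creatinine (mg/dL) | Pairs at or below 40 mL/min | Of these, below 30 mL/min |
|---|---|---|
| 2.0 | 38 of 42 | 16 |
| 1.5 | 16 of 42 | 1 (75 y, 55 kg) |
| 1.2 | 3 of 42 | 0 |

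These are grid cells, not patients. They show whom the rule can admit, not how many would enrol.

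**Step 4: match admitted patients to instructions.**

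| Clearance (mL/min) | Eligible under criterion 14? | 8.2.3 | 8.2.6.3 |
|---|---|---|---|
| 51–80 | Yes | No change | Careful monitoring (mild impairment) |
| 40–50 | Yes | 75% of starting dose | Reduction required |
| 30–39 | Yes, if creatinine ≤ 2.0 | Nothing | Reduction required, no amount, wrong cross-reference |
| Below 30 | Yes, if creatinine ≤ 2.0 | Nothing | Higher exposure noted, no dose and no prohibition |

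The 40 mL/min limit in criterion 14 coincides with the lower end of the band in 8.2.3. That suggests 40 was the intended floor, although this is an inference. The 'or' does not enforce it.

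**The case against.** The strongest reply is that the protocol is less silent than it looks.

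- **30–39 mL/min.** Section 8.2.6.3 counts this range as moderate impairment and requires a reduction, and 8.2.3 contains only one starting-dose reduction for moderate impairment, 75%. A careful reader could join the two. That is fair: in this band the defect is two conflicting definitions and a wrong section number, not a missing safeguard. But the text that gives the amount limits itself to 40–50.
- **Below 30 mL/min.** Investigators are made responsible for consulting the current package insert, which is a reasonable arrangement for a commercially supplied comparator. Exclusion 14 still applies when criterion 14 is met. The insert is not among the documents, so actual harm cannot be shown from them. All of this stands. Yet neither safeguard puts a renal threshold in the protocol, and criterion 14 tells the investigator that renal function is adequate.
- **Monitoring.** Chemistry is scheduled on Day 1 of each cycle and haematology also on Days 7 and 14 of Cycle 1, and 8.2.6.3 recommends prompt interruption for grade 2 to 4 events. This limits the consequences, but beyond the Cycle 1 Day 1 pre-dose check it acts only after capecitabine has been started.
- **Likelihood.** The largest counts sit at the 2.0 mg/dL ceiling, the ages and weights are assumed, and only about 100 of 300 patients receive capecitabine. The number affected may be small. This limits what can be said about frequency but does not remove the gap.
- **Cost to the other arm.** A floor of 40 would also exclude such patients from CDX-011, whose dosing section is not in the supplied text. The restriction cannot be judged for that arm. However, eligibility is settled before randomisation, so every entrant must be fit to receive either drug.

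**Conclusion.** The concern holds. As written, criterion 14 admits patients with clearance below 40 mL/min, and some below 30, on creatinine alone. Explicit starting doses stop at 40, and below 30 the protocol reports higher capecitabine exposure without saying what to do. For a 65-year-old, 60 kg woman, the range of creatinine that qualifies despite a clearance of 40 or less runs from 1.33 to 2.0 mg/dL; above 1.77 she is below 30 mL/min.

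Confidence is high on the wording and the arithmetic, which use only the protocol's limits and formula with assumed ages and weights. The number of patients affected is unknown. The point should be fixed on safety grounds, and it has no bearing on the primary analysis.

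**What to change.** In the synopsis and in 7.2.2.1, require calculated creatinine clearance above 40 mL/min for every patient, either by changing 'or' to 'and' or by dropping the creatinine limit. Every admitted patient with renal impairment then falls in a band that 8.2.3 covers.

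If the clinical team prefers to admit patients at 30–39 mL/min, set the floor at 30 and extend the 75% starting dose in 8.2.3 to 30–50 mL/min. The choice between the two floors is clinical; either closes the gap.

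In both cases, use one definition of moderate impairment in 8.2.3 and 8.2.6.3, and change the cross-reference in 8.2.6.3 from 8.2.2 to 8.2.3.

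The cost is a protocol amendment with its ethics approvals across the planned 100–175 centres, and possibly a few more screening failures in both arms. No new tests are needed, because creatinine, age and weight are already collected at screening. The 203 events and 300 patients stay as they are.

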7.2.2.2. Exclusion Criteria

Patients will be excluded from the study for any of the following reasons:

1. Progression/recurrence of breast cancer during or within 3 months of completion of neoadjuvant or adjuvant chemotherapy.
2. Investigational therapy within four weeks before planned start of study treatment.
3. Persistent neuropathy $>$ NCI-CTCAE v. 4.0 Grade 1 (at randomization).
4. History of allergic reactions attributed to compounds of similar composition to dolastatin or auristatin. Compounds of similar composition include Auristatin PHE as an anti-fungal agent, Auristatin PE (TZT-1027, Soblidotin, NSC-654663) as an anti-tumor agent and symprostatin 1 as an anti-tumor agent.
5. Known hypersensitivity to 5-fluorouracil, capecitabine or any of its components.

^b Also referred to as CEN17.

6. Known dihydropyrimidine dehydrogenase (DPD) deficiency.
7. Known brain metastases, unless previously treated and asymptomatic for 2 months and not progressive in size or number for 2 months prior to randomization. Continued use of steroids and/or anticonvulsants (in the absence of any suspicion of progressive brain metastases) is acceptable.
8. Subjects unable to provide informed consent and/or unable to comply with the study procedures.
9. Pregnant or breast-feeding women, and women or men who are not willing to use effective contraception during the time from signing of informed consent through two months after the last dose of study treatment. Effective contraception is defined as double barrier contraception (e.g., condom plus spermicide in combination with a female condom, diaphragm, cervical cap, contraceptive sponge or vaginal ring), intra-uterine device (IUD), implants, injectables, combined oral contraceptives, sexual abstinence (total abstinence from sexual intercourse as the preferred lifestyle of the subject; periodic abstinence is not acceptable), or sexual intercourse with only a vasectomized partner. Patients and/or partners who are surgically sterile or postmenopausal are exempt from this requirement.
10. Previously received capecitabine and discontinued due to progressive disease or intolerance; previously received CDX-011(CR011-vcMMAE; glembatumumab vedotin) or other MMAE-containing agents. ~~{criterion deleted}~~
11. Active systemic infection requiring treatment. Infection controlled by oral therapy will not be exclusionary. Note: microscopic examination of urinalysis is required during screening. If urinary infection is suspected, then a negative urine culture is required prior to enrollment. ~~{criterion deleted}~~
12. Chronic use of systemic corticosteroid above the physiologic dose (5 mg per day prednisone or equivalent) within 7 days of enrollment, except for premedication. ~~{criterion deleted}~~
13. Significant cardiovascular disease including unstable angina pectoris, uncontrolled hypertension, and congestive heart failure (New York Heart Association class 3 or 4), a history of a serious uncontrollable arrhythmia despite treatment, ischemic or severe valvular heart disease, or a myocardial infarction within 6 months prior to the trial entry.
14. Any underlying medical condition that, in the investigator's opinion, will make the administration of study treatment (CDX-011 or capecitabine) hazardous to the patient, or would obscure the interpretation of adverse events.
15. Other malignancy except for adequately treated and cured basal or squamous cell skin cancer, curatively treated in situ disease, or any other cancer from which the patient has been disease-free for ≥ 5 years.

